1. PURPOSE OF THE STUDY

a. Brief Summary

This study aims to test the effectiveness of an evidence-based eating-disorder prevention program specifically targeted for individuals with Type 1 Diabetes (T1D) compared to an educational control group. The Diabetes Body Project (DBP), is an adaptation of the Body Project which is the only eating disorder prevention program to have repeatedly produced effects when evaluated by independent researchers, produced stronger effects than credible alternative interventions, and affected objective outcomes. DBP has been adapted slightly for individuals with T1D who are at ultra-high risk for eating disorders. The study aims to test the effectiveness of the DBP of reducing body image concerns and reducing eating pathology and improving glycemic control.

b. Objectives

Aim 1 is to test the hypothesis that participants who complete the Diabetes Body Project will show significantly greater improvements in glucose control (HbA1c and Time in Range [TIR]), the primary outcomes, as well as reductions in diabetes distress, illness perceptions, and quality of life (secondary outcomes) over follow-up than control participants who view educational lectures of diabetes management and EDs. Although HbA1c is the most common measure of long-term blood glucose management (ADA, 2018), with the advent of continuous glucose monitoring (CGM), the ability to classify sensor glucose levels into various ranges has been feasible. Time in Range (TIR), which reflects the amount of time an individual had glucose values between 70 and 180 mg/dL, has shown a robust inverse association with development of diabetic retinopathy and microalbuminuria (Beck et al., 2019). As of July 2022, we are making the CGM optional, this will decrease our power to detect changes in TIR.

Aim 2 is to test the hypothesis that Diabetes Body Project participants will show significantly greater reductions in ED risk factors (pursuit of the thin ideal and body dissatisfaction), ED behaviors (dietary restriction, insulin omission), and ED symptoms (additional secondary outcomes) than control participants, and whether reductions in ED outcomes correlate with reductions in HbA1c and increases in TIR and mediate the effects of the Diabetes Body Project on improvements in HbA1c and TIR. If this pilot study shows that the Diabetes Body Project is effective in decreasing eating disorder symptoms and behaviors in this population than it would provide support for a larger trial testing the effectiveness of DBP and the dissemination of DBP thereby helping to decrease eating disorder symptoms and increase quality of life and overall health of individuals with T1D.

c. Rationale for Research in Humans

The purpose of this study is to test the effectiveness of an eating disorder prevention program, the Diabetes Body Project.

2. STUDY PROCEDURES

a. Procedures

Participants will be recruited through flyers, online postings, and other postings at various clinics treating Type 1 Diabetes (T1D) in the Bay Area. To determine eligibility, during screening participants will be asked their age, gender, how long they have had T1D, if they are taking insulin, if they have visited their diabetes care provider in the past year, and basic questions assessing body dissatisfaction.

On the flyers and other recruitment materials, participants will be directed to a short survey on a secure platform that only asks for contact information (see section 16) to show interest in the study. The study team will use the contact information provided to set-up a phone screen for interested individuals. IF the participant shows interest through one of the Honest Broker methods (such as MyChart) or through ResearchMatch.org which shares the contact information with the research team, then a member of the research team will reach out to the individual using the contact information provided to thank them for their interest and schedule a phone screen. See section 13 for the phone screen.

For participants who are under the age of 18, we will complete the phone screen with the parent. During this phone screen, we will ask for permission to contact the adolescent to conduct the same phone screen. The second phone screen with the adolescent will be to establish rapport with the study coordinators and to make sure we know the level of self-reported body dissatisfaction from the adolescent, as it is unlikely the parent will know the level of body dissatisfaction the adolescent experiences. After the participant completes the phone screen, a member of the study team will contact them to confirm eligibility. Informed parental consent and adolescent assent (for ages 15-17) or consent (for ages 18- 30) will be secured prior to enrollment. If an adolescent turns 18 during their participation in the study, they will be consented at their first assessment or group session after turning 18.

Baseline Assessment: After eligibility is confirmed but before groups begin, the research assistant will email participants a Redcap link to complete the surveys for baseline assessment. At the baseline assessment, participants will complete a survey involving the following questionnaires:

1) the 8-item Ideal-Body Stereotype Scale-Revised (Stice et al., 2017) which assesses pursuit of the thing ideal

2) the 9-item Body Dissatisfaction Scale (Berscheid et al., 2973) which assesses dissatisfaction with various body parts

3) the 16-item Diabetes Eating Problem Survey-Revised (Markowitz et al, 2010)

4) the 28-item Type 1 Diabetes Distress Scale (Fisher et al., 2015) which assesses distress related to diabetes

5) the 5-item World Health Organization Well-Being Index (deWit et al., 2007) that assess health related quality of life

6) Negative affect will be assessed with the sadness, guilt, and fear/anxiety subscales (totaling 20 items) from the Positive Affect and Negative Affect Scale-Revised (PANAS-X; Watson & Clark, 1992)

7) 10-item Dutch Restrained Eating Scale (van Strien et al., 1986) that measures dieting behaviors.

At the baseline assessment, participants will also complete an Eating Disorder Diagnostic Interview (EDDI) over the phone. The EDDI can take between 30 to 60 minutes to complete depending on the number of behaviors endorsed by the participant. The EDDI will be administered by a trained research assistant. At baseline, participants will also be asked to report their A1Cs. We will only ask for self-reported A1Cs.

For the last part of the baseline assessment, Glucose monitoring data will be collected via glucose monitors that are already in use, among participants already using these devices at the time of enrollment, with data being shared by the participant with the research team via secure online portals created and run by their corresponding device company. For participants who are not already using glucose monitors at the time of enrollment, they will be given the option of us sending them one. If they agree to wearing a CGM then a Libre 2 glucose monitor devices will be provided by study staff, as well as training on use following FDA-approved self-start guides that are available online. See section 16 for the Libre 2 informational brochure. However, if a participant does no already have a CGM and does not want to wear one, then we will not send them one. This means they will not receive the \$25 at baseline and at the 3-month follow-up that is set aside for the two-week CGM information. They will be made aware of this when they decide not to wear the Libre2. The CGM is invasive, but it is a quick process that participants do at home. It is quick and often painless. Also in section 16 is a link to a video illustrating how to apply the sensor. Research staff will also provide support throughout use, and will be used to collect 2 weeks of data at each time point.

Prevention Program:

After baseline assessments are completed, participants will be randomized to either the Diabetes Body Project groups or the educational control.

Randomization:

We will use a random number generator to determine if participants will be in Diabetes Body Project or the educational control. If an even number is generated, the participant will be assigned DBP. If an odd number is generated, the participant will be assigned to educational control. As there is a 50% chance the number will be either even or odd, there is a 50% chance that someone will be assigned either to DBP or the educational control. It is only after the baseline assessment that individuals will be randomized. This will prevent the assessor at baseline from being influenced by which group the participant will be in. The assessor completing the EDDI at post-test and 3-month follow-up will be blind to the participant's condition.

Diabetes Body Project: The Diabetes Body Project is an adaptation of the Body Project. The original Body Project involves weekly 1-hour sessions for 4 weeks. The adapted version includes weekly 1-hour sessions for 6 weeks. Sessions will be co-led by a clinician and a peer educator with Type 1 Diabetes. The adaptation involves diabetesspecific content in the sessions as well as the inclusion of a peer educator with Type 1 Diabetes. In session 1 participants volunteer to participate verbally in the session, collectively define the thin appearance ideal, discuss costs of pursuing this ideal, and are assigned home exercises (e.g., write a letter to a younger girl about the costs associated

with pursuing the thin ideal). In session 2 participants discuss each home exercise, dissuade facilitators from pursuing the thin ideal in role-plays, and are assigned more exercises (e.g., generate a top-10 list of things young women can do to challenge the thin ideal). In session 3 participants discuss home exercises, conduct role-plays challenging thin-ideal statements, discuss personal body image concerns, and are assigned home exercises (e.g., engage in two activities that challenges the thin ideal). In session 4 participants discuss home exercises, discuss the negative effects of social comparison, the advantages and costs of social media, and are assigned home exercises (e.g., track situations in which they engage in social comparison and state alternative ways of thinking). In session 5 participants discuss home exercises, discuss strategies of living well with diabetes and maintaining good self-care, as well as the physiological and psychological advantages of insulin, and are assigned home exercises (e.g., writing a letter to a younger girl with T1D with advice on having a positive relationship with her diabetes). In Session 6 participants review each home exercise, discuss the benefits of the group and what was learned, and how to continue some of the exercises introduced in the Diabetes Body Project; as a final home exercise, participants are encouraged to engage in at least one more self-affirmation exercise and email the facilitators to tell them how it went. This is different from standard of care, as most times individuals with Type 1 Diabetes don't have the opportunity to discuss body image concerns and eating pathology, especially specifically in relation to Type 1 Diabetes. This is the first eating disorder prevention program designed specifically for this high-risk population. Participants will continue to receive usual care from their diabetes care team during their participation in the study

Educational Control:

We selected a T1D management/ED psychoeducational comparison condition previously tested (Olmsted et al., 2002) to control for expectancy effects and demand characteristics. To match the Diabetes Body Project, the educational lectures by [name] will be delivered in 6 1-hour blocks. Topics include basic information about the various eating disorders, complications of ED behaviors, diabetes and body image, effects of dieting on blood glucose, and the risk of complications. Strategies to develop a healthy relationship with food, how to overcome binge eating and purging behaviors (including intentional insulin omission), and how to improve body image are also discussed. If participants are randomized to the Diabetes Body Project, they will meet in groups of 6 individuals co-led by a peer educator with T1D and a clinician. Groups will meet once a week virtually for an hour, for six weeks. Each week involves homework that participants are asked to complete before the next session. If participants are assigned to the Education intervention, they will be asked to watch one-hour of videos including information about diabetes management and eating disorders each week for six weeks. Post-Test:

After the six weeks of either Diabetes Body Project or the educational control, participants will be asked to complete the same questionnaires that they assessed at baseline and the EDDI.

3-Month Follow-up:

At 3-month follow-up, participants will again complete the questionnaires and the EDDI, but will also wear the continuous glucose monitor (either the one they already have or the

Libre 2 provided by the research staff) and be asked to self-report A1c. After the 3-month follow-up, participants have completed all study responsibilities.

b. Procedure Risks

These research procedures provide minimal risk to subjects. We are Using current and empirically evaluated measures and research staff available who have been fully trained both in administrating physiological interviews. The Body Project has also been tested in multiple trials and has produced only positive effects, there has been no history of symptoms worsening as a result of participating in the program. The above procedures present minimal risk. Engaging in the intervention modules carries minimal risk for emotional discomfort or stress. Subjects will have the option of not participating in conversations or exercises in the intervention modules that cause them any discomfort. They will also be free to withdraw from participating in the intervention and/or overall study at any time. Survey measures are non-invasive and present minimal risk. Glucose monitors are minimally invasive and provide no added level of risk or discomfort beyond routine diabetes management tasks.

Adolescent and caregiver participants will be advised of their rights to withdraw from the intervention at any time without penalty or consequence on their receipt of future health care services at Stanford University's Lucile Packard Children's Hospital or affiliated clinics.

c. Use of Deception in the Study

Deception will not be used.

d. Use of Audio and Video Recordings

Participants will be informed that we will make video recordings of the Diabetes Body Projects groups for clinical supervision and quality assurance purposes. These recordings will be reviewed by the primary investigator to assess intervention fidelity and therapeutic competence of the group leaders. Email supervision based on these ratings will be provided to facilitators which has been found to maximize intervention effects. After they are viewed and rated for fidelity and competence, all records of the recordings will be deleted from devices and destroyed. Recordings are not optional. As the group sessions are virtual and conducted via Zoom, it is impossible for someone to "go out of view of the camera" and recording is an important part of the intervention. Also, recording is an important part of the intervention so turning off their camera on Zoom is not an option. There are three main factors that increase cognitive dissonance: public accountability, level of effort, and voluntary basis. By recording the sessions, public accountability is greatly increased and the effect of the intervention improves. Thus, if they are in DBP individuals must be willing to be recorded.

e. Alternative Procedures or Courses of Treatment

Currently, there are not any eating disorder prevention programs specifically designed for individuals with Type 1 Diabetes. Therefore, no standard treatment is being withheld from participants.

f. Will it be possible to continue the more (most) appropriate therapy for the participant(s) after the conclusion of the study?

If the Diabetes Body Project (DBP) produces significantly larger improvements than the educational lectures, we will offer the DBP to educational controls.

g. Study Endpoint(s)

It is important to test whether effects persist at 3-month follow-up even if there are good effects at posttest, as it is possible that the effects may not persist. The effects of this brief prevention program typically have shown good persistence through 1- to 2- year follow-ups but tend to fade partially by 4-year follow-up.

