Participants will also be recruited through online flyers sent out through established diabetes-related listervs run by diabetes organizations.

The IRB-approved recruitment flyer and email will also be circulated through online websites, forums newsletters, emails listervs, and social media pages (primarily run by diabetes organizations such as DYF and JDRF) and shared with diabetes providers and clinics within and outside of Stanford. These online avenues are often used to disseminate information to families of youth with type 1 diabetes offering various information and resources, including opportunities to participate in studies similar to the current study.

We will partner with the Research Participation team for Honest Broker outreach. Potential participants are identified via STARR and invited by Research Participation team (honest broker) on behalf of study team. See Section 16 for Honest Broker study invitation letters. We will be using Children's Epic MyChart, Postal Mail honest broker outreach. For Epic MyChart, study team receives only the interested responses via Epic MyChart InBasket. For Postal Mail, study team may support the process by sticking preprinted address labels (created by honest broker) on the envelopes. Invitations will not be sent to the same individual via more than one honest broker outreach method, unless as a separate reminder.

The Research Participation team informed us of Study Pages. We are going to be part of the University's pilot program with Stanford. They are testing Study Pages with 100 studies to see if it helps with recruitment and outreach. Through the StudyPage we can text and call participants in a HIPPA-compliant manner. We can also schedule participants.

h. Eligibility Criteria

i. Inclusion Criteria

I)female-identifying
II) aged 15-30 years old
III) diagnosis of T1D for at least a 6-month duration per ADA criteria who are taking insulin
IV) have visited their diabetes care provider in the past year
V) body image concerns

ii. Exclusion Criteria

I) not female identifying
II) not in age range
III) does not have a diagnosis of T1D for at least 6 months per ADA criteria
IV) not taking insulin
V) have not visited their diabetes care provider in the past year
VI) do not report some level of body dissatisfaction
VII) do not live in the United States
VIII) Unwilling to be video-recorded if assigned to Diabetes Body Project

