IX) restricted English proficiency, and pervasive developmental, cognitive, or psychiatric limitations that compromise participation in the intervention sessions and study.
Glucose monitors will be provided to participants who are not already using these

Glucose monitors will be provided to participants who are not already using these devices such that device use will not be a criterion of eligibility or exclusion.

i. Screening Procedures

Participants will indicate interest by completing a short survey on a secured platform, such as REDCap, that asks them for contact information. From there, a member of the research team will contact them to conduct the telephone screening where verbal consent will be obtained. For adolescents, a member of the research team will first screen the parent and ask them about the adolescent. We will ask the parent for verbal consent to contact the adolescent to ask similar questions. A second phone screen will occur with the adolescent where verbal assent will be obtained. The second phone screen serves to increase rapport and to obtain the adolescents own body image concerns.

j. Participation in Multiple Protocols

As a part of the informed consent process, subjects will be asked if they are participating in any other research projects. Their participation in other protocols will not exclude them from participation in this study.

k. Payments to Participants

Participants will be paid \$15 for the pretest assessment, \$20 for the posttest, and \$25 for the 3-month follow-up assessment (baseline, post-test, and three-month follow-up) and \$25 for each complete wear of glucose monitoring. In total, then, participants could receive \$110. They will be paid for whatever portions of the study they complete (i.e., it is prorated). If they do not wear the CGM/provide CGM data, total possible payout is \$60.

I. Costs to Participants

There will be no cost to participants.

m. Planned Duration of the Study

It is estimated that the study will take one year. The screening is expected to take 10-15 minutes. Active participation will last about 5 months. Participants will complete the baseline assessment (1.5 hours), then wear the CGM for two weeks, then complete the six-week intervention (each session is one hour), and then a post-test assessment (about 1.5 hours). After the initial baseline assessment, intervention, and the post-test

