participants will have completed all necessary tasks until the 3-month follow-up where they will complete the same tasks as the baseline assessment and where the CGM for two weeks. While the groups are running, data analysis on baseline data will begin. Once we have complete data for posttest and 3-month follow-up, we will conduct data analysis on the outcome measures.

5. **RISKS**

a. Potential Risks

i. Investigational devices

None

ii. Investigational drugs

None

iii. Commercially available drugs, biologics, reagents or chemicals

There are no risks of commercially available drugs, reagents, or chemicals as none will be used.

iv. Procedures

Data Collection: Self-reported survey will be kept confidential and collected online via secure RedCap database system. The diagnostic interviews will require phone numbers as they will be conducted over the phone, but the interview forms will only be labeled with the participant ID number. All stored and collected interview data will not include names or phone numbers. There are no known psychological risks to subjects completing self-report subjective rating scales or participating in the intervention sessions. However, the survey and intervention may contain items or questions that make the subjects feel uncomfortable in that they ask about their physical and psychological health and feelings/emotions. Subjects will be informed that any items on questionnaires or topics discussed in the intervention modules that produce these effects may be skipped or ignored.

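### The SAP states no workable model for HbA1c, a primary outcome that the protocol collects only as undated self-report at baseline and 3 months

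*Protocol*

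**What the plan says.** **Status of the outcome.** Protocol 1b names "glucose control (HbA1c and Time in Range [TIR]), the primary outcomes".

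**How it is obtained.** At baseline (Protocol 2a): "We will only ask for self-reported A1Cs". At the 3-month follow-up (Protocol 2a): "Libre 2 provided by the research staff) and be asked to self-report A1c". Section 4m agrees that participants have nothing further to do "until the 3-month follow-up where they will complete the same tasks as the baseline assessment". At post-test, by contrast, "participants will be asked to complete the same questionnaires that they assessed at baseline and the EDDI"; no A1c request is listed there.

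**What governs the age of a result.** The study schedules no A1c test. Section 2a says "Participants will continue to receive usual care from their diabetes care team during their participation in the study", with no testing interval. The only recency rule is an entry criterion in section 4h, that participants "have visited their diabetes care provider in the past year". For CGM, section 2a does define the measurement: two weeks of data at each time point.

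**What the SAP says.** Every outcome other than TIR gets a linear mixed model with the pretest score, treatment group (five groups, or control), assessment (post-test or follow-up), the condition-by-assessment interaction and a random intercept per participant. TIR gets a regression of the 3-month value on the pretest value and treatment group, because it was not measured at post-test. Post-test missingness is given as 11% to 15%, naming EDS, TII, BD, DD and QOL. Missing data are handled by full information maximum likelihood under missing at random. HbA1c is not mentioned.

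**The concern.** On the protocol's schedule, HbA1c is in the same position as TIR: one baseline value and one 3-month value. The SAP makes an exception for TIR and none for HbA1c, so by default HbA1c falls under a model that its data cannot support. A reader cannot tell how, or whether, this primary outcome was analysed.

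The second issue is what the 3-month value represents. A participant asked for an A1c can give only the latest result she has. With no date, maximum age or window, that result may come from before randomisation, and one result could be reported at both time points. Such a value cannot respond to treatment. Maximum likelihood for missing data does not help, because the value is present.

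Both matter more because CGM became optional in July 2022, and the protocol concedes that this lowers power for TIR. For a participant without CGM data, self-reported HbA1c is the only primary outcome.

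**Working it through.** The documents give no sample-size calculation, HbA1c effect size or standard deviation, so there is no stated figure to reproduce. Three checks apply.

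**1. Can the SAP's default model be fitted to HbA1c?**

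For participant *i*, write the model as

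y = b0 + b1·pretest + Σ g_k·D_k + b2·A + b3·(C × A) + u + e,

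where D_1 to D_5 mark the five treatment groups, C is condition (0 or 1), A is assessment (0 post-test, 1 follow-up), u is the random intercept and e the residual. The fixed part has 1 + 1 + 5 + 1 + 1 = 9 coefficients.

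If A1c exists only at follow-up, A = 1 on every record. Then:
- A equals the intercept column, so only b0 + b2 is estimable.
- C × A equals C, and C = D_1 + … + D_5, so only the five sums g_k + b3 are estimable.
- Each participant has one record, so var(u) and var(e) cannot be separated; only their sum is estimable.

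That leaves 1 + 1 + 5 = 7 estimable combinations of the 9 fixed coefficients, and one variance instead of two. What remains is a regression of the 3-month value on the baseline value and treatment group, which is the model that the SAP gives for TIR. Full information maximum likelihood cannot restore the lost terms, because no participant would have a post-test value.

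**2. Do the SAP's missingness figures cover HbA1c?**

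The highest post-test figure is 15%. An outcome not requested at post-test would be about 100% missing there. Either the ranges omit HbA1c, or a post-test A1c was collected that the protocol does not list.

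**3. When is a reported result pre-treatment?**

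- The programme lasts 6 weeks (Protocol 2a). Counting the follow-up as 3 months (13 weeks) after it, programme start is 6 + 13 = 19 weeks before follow-up.
- Adding the 2-week baseline CGM wear (section 4m), baseline is 2 + 6 + 13 = 21 weeks before follow-up if there is no waiting time. This fits section 4m: "Active participation will last about 5 months".
- Randomisation follows the baseline assessment, so it falls no later than programme start. A result more than about 19 weeks old at follow-up predates the programme; waiting for a group to form would move randomisation further back.

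If a share f of follow-up values in each arm carries no treatment effect, the expected difference is multiplied by (1 − f).

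*Illustration only.* The documents give no testing interval. Suppose tests are L weeks apart and the age of the last result at follow-up is uniform on 0 to L. The share drawn before programme start is f = max(0, 1 − 19/L):

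| Assumed L (weeks) | f | Multiplier 1 − f |
|---|---|---|
| 13 or 19 | 0 | 1.00 |
| 26 | 1 − 19/26 = 0.27 | 0.73 |
| 52 | 1 − 19/52 = 0.63 | 0.37 |

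The share drawn before randomisation is no larger than f. The table shows how strongly the answer depends on an interval that nobody has stated. It does not estimate what happened in this trial.

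**The case against.** The strongest reply is that the documents do not show any harm. The SAP is in the past tense, reports observed missingness and never mentions HbA1c. A reader might infer that stale results were analysed as 3-month values. That does not follow: the text does not show that any HbA1c value was analysed. It shows only that nothing prevents such use. Nor does silence in the SAP establish that HbA1c was abandoned or withheld.

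A reader might also take the past-year visit criterion as evidence of yearly testing, and so expect large dilution. It is an entry minimum about visits, not about A1c tests. Recruitment includes three clinics specialising in type 1 diabetes, although it also uses wider online sources. With results no more than about 19 weeks old, no follow-up value would predate the programme.

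The survey forms are not in the supplied text. A test-date field may exist, and an A1c item may sit inside the questionnaires repeated at post-test. If so, the mixed model might be estimable, and the protocol's description of post-test would be what needs correcting. This stands as a limit. It does not remove the mismatch between the two documents as written, or supply a stated window or rule.

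Finally, dates recovered after the fact would be imperfect, participants have finished their study tasks, and some enrolled as minors. That limits what can be asked of them now and is a reason to keep the remedy small.

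**Conclusion.** The point holds, in two parts of unequal firmness.

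The firm part is the analysis model. As written, the SAP's rule for outcomes other than TIR does not fit the protocol's A1c schedule, and a primary outcome has no stated, estimable analysis. This rests only on the two texts and on A1c being absent at post-test, as Protocol 2a indicates.

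The less certain part is the dating of results. The lack of a stated date, window or out-of-window rule is clear; its effect cannot be sized from the documents and may be near zero under frequent usual-care testing. If stale values are unrelated to arm, they bias the difference toward zero. If retesting depends on arm, the direction cannot be predicted. Baseline A1c, which would be the covariate, is equally undated.

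The sponsor should correct this. Confidence is medium, because the forms are not available and the number of affected values is unknown.

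**What to change.** 1. **Name the HbA1c model.** State in the SAP that HbA1c is analysed as TIR is, by regressing the 3-month value on the baseline value and treatment group, and report its missingness at both time points. If a post-test A1c was in fact collected, reconcile the protocol's post-test description instead. Cost: a few sentences and no loss of information, since this regression is all that the listed data can support.

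2. **Describe and date the measure.** Label the outcome self-reported HbA1c. Record the test date with each report, or use dates already captured. Report by arm how many follow-up values predate randomisation and how many participants gave the same result twice, noting that equal values can also arise by chance. Report the age of baseline values. Add one sensitivity analysis that sets follow-up values drawn before randomisation to missing. Cost: one item per report, or retrieval of existing dates; some loss of precision and possible selection (retesting may depend on arm), confined to that sensitivity analysis.

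3. **If dates are unavailable,** state that a null HbA1c result may partly reflect stale values. Cost: one sentence.
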